#### **6.1.1 Data Collection**

As this is a pilot study, we will gather a convenience sample of 100 participants who are eligible to be referred for outpatient cognitive assessment (50 from each site) will be evaluated. Data will be collected by telephone interview follow-up and chart review for observational characterize subjects, sites, processes, utilization, and outcome endpoints.

Research staff at both sites will contact by telephone the selected participants to conduct two focused interviews at 1-6 weeks and 3 months post-ED visit. The survey will assess the participants experiences through the process, findings of the assessment and the participants follow-up care plan. A retrospective chart review will be conducted on these participants. Trained research staff at each site will conduct chart review in the Electronic Medical Record to determine rates of:

- Healthcare utilization by the patients during the subsequent 30 days in addition to the requested outpatient cognitive assessment, inpatient hospitalizations, and/or ED revisits up to 6 months prior to the current ED visit

- Referral and completion of outpatient cognitive assessment
- New outpatient diagnoses of Alzheimer's Diseases or Related Dementia diagnoses or mild cognitive impairment
- Documentation of Outpatient Cognitive Assessment communication with the patients' primary care providers or other consults of results and recommendations for brain health treatment and management.

Trained research assistants will review the medical records of potentially eligible participants seen in the ED during the study period to assess clinician compliance and acceptance of screening intervention.

Data for this study will be collected, recorded and stored using Redcap (Research Electronic Data Capture). Redcap is a secure, web application designed to support data capture for research studies. Data from any paper study forms will be entered into Redcap and then stored in locked file cabinets restricted to the study team. Data coordination, data management, and database design will occur within the Yale School of Medicine's Program on Aging. See Table 1 for data points that will be collected.

Retrospective chart review will be conducted on a subset of 100 patients as part of study enrollment: We will collect data on a subset of patients meeting inclusion criteria (50 from each site, for a total of 100 subjects).

Assessment	Screening: Visit (Day 0)	Enrollment: Telephone follow-up #1 (Day 1-45)	Telephone follow-up #2 (Month 3)	Chart Review
ESI level	X			X
ED chief complaint				X
Demographics	X			X
Comorbidities	X			
Disposition from ED (discharged or admitted)	X			X
Discharge to community	X			X
Delirium Screen	X			X
Memory or thinking problem in prior year	X			X
ED referral for outpatient cognitive evaluation requested	X			X
Outpatient appointment scheduled		X	X	X
Outpatient appointment completed		X	X	X
Outpatient cognitive assessment batteries		X	X	X
New Outpatient Cognitive Impairment Diagnoses		X	X	X
Primary Care Brain Health Communication Coordination		X	X	X
Healthcare Utilization		X	X	X
Adverse Events		X	X	X

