### Study Design

The study is observational consisting of telephone interviews and medical record review.

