#### **4.1 Study Duration**

This study will last for 2 years. The expected duration of subject participation will be approximately 3 months, starting from the date of initial ED evaluation. We anticipate 6 months of subject enrollment and follow-up and then 18 months of data collection, preparation, and analysis.

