#### **Standard Care for Outpatient Cognitive Assessment Referral**

The outpatient clinics receiving the ED referrals will reach out to patients to establish and schedule an outpatient evaluation after discharge from the ED.

As part of routine care, the outpatient assessments may include brief neuropsychological tests of cognition memory, language, executive function and attention that may include the Montreal Cognitive Assessment (MoCA), a cognitive screening test to aid in detecting cognitive impairment and evaluations to assess competency in completing instrumental activities of daily living such management of money, behavioral deficiencies and others for standardized consensus evaluation for diagnosis of dementia, cognitive impairment or normal with subtype of impairment. The outpatient evaluations will allow for clinical diagnosis and validation of ED assessment for the presence of dementia or mild cognitive impairment.

In addition, following the evaluation, the outpatient centers will document cognitive impairment diagnoses (if present) and notify patients, caregivers and their primary care providers of results. The centers will utilize available resources to connect patients to their primary care provider with feedback and recommendations for brain health care and management.

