#### **7.2 Planned Analyses**

This is an observational study that will evaluate the feasibility of implementing a brief training and assessment protocol to assess for undiagnosed cognitive impairment and dementia in ED patients and refer those at risk for outpatient evaluation. The ED assessment protocol, referral process, and outpatient evaluation will be integrated into clinical care. Researchers will gather observational data about these processes to measure the proportion of patients who are at risk in the emergency department, number of patients who are referred to the outpatient setting up to 3 months post-discharge and number of patients who evaluated who are diagnosed with cognitive impairment. These sample sizes will provide estimates needed for future larger scale pragmatic evaluation of such clinical care and its impact on patient and caregiver outcomes.

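### The first research call asks about the cognitive appointment while booking and attendance are still open, so the later referral rates may exceed what the routine pathway alone would give

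*Combined protocol and SAP*

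**What the plan says.** The Synopsis describes the design in these terms: "The study is observational consisting of telephone interviews and medical record review". The pathway being observed is set out in section 6.1 under standard care: "The outpatient clinics receiving the ED referrals will reach out to patients to establish and schedule an outpatient evaluation after discharge from the ED". No research contact is part of it.

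Section 6.1.1 then has research staff at both sites telephone the participants to "conduct two focused interviews at 1-6 weeks and 3 months post-ED visit". On content it says: "The survey will assess the participants experiences through the process, findings of the assessment and the participants follow-up care plan". Table 1 heads the first call "Enrollment: Telephone follow-up #1 (Day 1-45" (days), so call 1 is also the enrolment contact. The row "Outpatient appointment completed" is marked at call 1, call 2 and chart review. So are the rows for appointment scheduling, new cognitive diagnoses, primary-care communication and healthcare utilization. The chart review covers the same participants who are telephoned.

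On the time horizon, section 4.1 states: "The expected duration of subject participation will be approximately 3 months, starting from the date of initial ED evaluation". Section 7.2 mentions the "number of patients who are referred to the outpatient setting up to 3 months post-discharge", which concerns referral. No end date is given for counting completed appointments.

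Section 3.3 sets the aim as feasibility in routine care, and section 7.1 says the results will feed the sample size, effect and power calculations of a later study.

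**The concern.** A patient with possible memory problems who has not yet booked, or has booked and may forget, is telephoned by research staff, has the study explained and is followed up about the cognitive appointment. That contact can act as a prompt, and it would not exist when the process runs as routine care. Everyone enrolled receives it, so the study has no unprompted completion rate of its own. Taking completion from the chart limits reporting error, but it does not undo a change in behaviour.

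At stake are the rates a later pragmatic trial would borrow: appointments booked and attended, new diagnoses and primary-care communication. Section 4.2.1 also makes successful outpatient referral a primary variable without defining it. If it means attendance, it is exposed too. The problem is separate from who agrees to enrol: it would affect the rate even in a representative sample.

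**Working it through.** The plan states no rate, precision or power figure for these outcomes, so there is nothing to reproduce. The check has four steps.

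**1. Is the outcome still open at call 1?** Take 3 months as 90 days (assumed).
- Window of 1-6 weeks (sections 5.5 and 6.1.1), days 7 to 42: 90 − 7 = 83 and 90 − 42 = 48, so 48 to 83 days remain.
- Window of Day 1-45 (Table 1): 90 − 1 = 89 and 90 − 45 = 45, so 45 to 89 days remain.

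At least half the period is left in every case.

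**2. How large could the effect be?** Let p be 3-month completion without a call and c the share of would-be non-completers who attend because of the call. Both are assumed. The model takes everyone as called and no one as deterred.

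Observed rate = p + (1 − p)c, so inflation = (1 − p)c.

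| p | c = 5% | c = 10% | c = 20% |
|---|---|---|---|
| 20% | 24% (+4) | 28% (+8) | 36% (+16) |
| 40% | 43% (+3) | 46% (+6) | 52% (+12) |
| 60% | 62% (+2) | 64% (+4) | 68% (+8) |

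The smallest value is 0.40 × 0.05 = 0.02 and the largest is 0.80 × 0.20 = 0.16.

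**3. How does that compare with sampling error?** The 95% half-width is 1.96 × √(p(1 − p)/n). At p = 0.40:
- n = 100: 1.96 × √(0.24/100) = 0.096
- n = 50 (one site): 1.96 × √(0.24/50) = 0.136

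At p = 40%, inflation of 12 points (c = 20%) exceeds the pooled half-width of 9.6 points. Inflation of 3 to 6 points (c = 5-10%) does not, but a larger sample would not reduce it.

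**4. Could uncalled referred patients reveal it?** Assume p = 0.40, 100 called and 300 uncalled (the 300 is an assumption), with a two-sided 5% test of two proportions. For c = 20% the rates are 0.52 and 0.40 and the pooled rate is (52 + 120)/400 = 0.43.
- Standard error under the null: √(0.43 × 0.57 × (1/100 + 1/300)) = 0.0572
- Standard error under the alternative: √(0.2496/100 + 0.24/300) = 0.0574
- Power = Φ((0.12 − 1.96 × 0.0572)/0.0574), about 0.56

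The same calculation gives 0.18 for c = 10% and 0.88 for c = 30%. With 100 uncalled patients the three values are 0.14, 0.40 and 0.72. Such a comparison would describe the difference and reliably detect only a large one.

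**What the plan does about it.** The documents contain no call script or neutrality rule, no split of events at the call date, and no analysis of completion in uncalled patients. Section 7 compares referred patients with all discharged older patients on demographic and clinical characteristics. Section 7.3 adds a descriptive comparison of all eligible subjects with the 100, without naming completion.

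**The case against.** The strongest reply is that this is a possibility, not a finding. Table 1 lists data items rather than question wording, and no questionnaire is provided. Both sites share one call window. Some reactivity is unavoidable when consent and interviews are done by telephone, and early contact limits recall loss in this population. Section 4.2 says the study tests no hypotheses. The Synopsis primary outcome, ED screening and detection, is fixed before any call. All of this stands, and it limits the point to a risk for the later outcomes.

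It does not remove the point. Supplying rates for a later trial is the pilot's stated purpose, and nothing planned would let a reader judge how far the call contributed.

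Four stronger readings are tempting, and the documents support none of them:
- *The rates will be inflated by a known amount.* Neither p nor c is given.
- *Site differences will reflect call timing.* Calls at week 1 and week 6 leave 83 and 48 days, a gap of 35 days, so this could happen. Nothing shows that the sites call at different times.
- *The plan counts completion to 3 months.* This is inferred from the length of participation and the timing of call 2. The 3-month wording in section 7.2 concerns referral.
- *Events before call 1 give the routine-care rate.* Follow-up is cut at the call, sometimes within days. Call timing may depend on how easily a patient is reached. The information sheet in section 5.4 may arrive before the call.

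The exposed group is also not fixed: section 5.1 requires an actual referral, while section 6.1.1 speaks of patients eligible for one.

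**Conclusion.** The point holds as a design risk. Every enrolled participant is contacted about the appointment while 45 to 89 days remain (Day 1-45 window, 90 days assumed), by a contact the routine pathway does not contain. Rates of booking, completion, new diagnosis and primary-care communication may therefore be overstated, as may successful referral if that means attendance. ED screening, detection and placing of the ED referral are not affected.

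The size cannot be determined from the documents. The illustrative 2 to 16 points rests entirely on assumed base completion of 20-60% and assumed prompting of 5-20%. This limits how the later rates can be interpreted and carried into a trial design; it does not invalidate the study.

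**What to change.** In sections 6.1.1 and 7:

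1. Abstract the booking date and the completion date from the chart, and record the date of call 1. State when chart ascertainment of completion ends.
2. Report by site the bookings and completions before and after call 1, with the distribution of call timing.
3. Label the 3-month completion rate as observed under study contact.
4. Present pre-call events only as a descriptive lower bound on completion without the call, not as the routine-care rate, for the reasons given under the objection.
5. Where the referral log (8.4), the attendance tracker (8.3) and the full-waiver EMR data (5.5) allow, report completion among referred patients who were not called. Call it descriptive: convenience sampling and consent also separate the two groups, so the difference would not isolate the effect of the call.

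Separately, reconcile the call 1 window between sections 5.5 and 6.1.1 (1-6 weeks) and Table 1 (Day 1-45). The upper limits differ by only 3 days; the lower limits are Day 7 and Day 1.

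The cost is a few dates per subject and one table. Section 5.4 already has the date of verbal consent documented, consent is taken by telephone at the enrolment call, and completion is already abstracted. Item 5 adds abstraction for uncalled patients where it is possible. The downside is a less favourable or more qualified completion figure.

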### Number of Participants

A total of 100 subjects (50 from each site) will be included to gather retrospective observational data via telephone follow-up and chart review. These data will provide estimates in rates of screening and referral for a pilot sample of ED patients to ascertain the feasibility. Additionally, we will compare differences in processes, utilization, and outcome endpoints across the two sites. The number of subjects will provide the needed information to inform a future pragmatic clinical trial proposal.

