##### **4.2.2 Secondary and Exploratory Outcome Variables/Endpoints (if applicable)**

The variables used to assess the secondary objectives include healthcare utilization, rates of outpatient evaluation, confirmation of outpatient assessment, new diagnoses of dementia or mild cognitive impairment (MCI), and changes in outpatient primary care.

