#### **5.2 Number of Participants**

All patients 65+ years in age seen in both EDs during the study period will be screened in the ED using clinical screening for UCID.

A convenience sample of 100 hundred subjects (50 from each site) will be included for retrospective and prospective observational data via chart review and interview to evaluate rate of UCID detection in the ED, rates of referral for outpatient evaluation, rates of confirmed cognitive impairment or dementia by the outpatient evaluation, and differences across the two sites with processes, utilization, and outcome endpoints.

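### Does the chart-review item on healthcare utilization mix 30 days after the ED visit with 6 months before it, leaving the outcome undefined?

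*Combined protocol and SAP*

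**What the plan says.** Section 6.1.1 (Data Collection) has trained staff at each site review the electronic record to obtain rates for four bulleted items. The first bullet begins "Healthcare utilization by the patients during the subsequent 30 days in addition to the requested outpatient cognitive assessment" and runs on, without a break, to "inpatient hospitalizations, and/or ED revisits up to 6 months prior to the current ED visit".

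The same section names telephone interview and chart review together as sources for utilization, and schedules "two focused interviews at 1-6 weeks and 3 months post-ED visit". Table 1 marks healthcare utilization at the first call (headed Day 1-45), at the second call (Month 3) and in an undated chart-review column. It has no mark at Day 0.

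Elsewhere utilization appears without a window. Section 4.2.2 states: "The variables used to assess the secondary objectives include healthcare utilization". The synopsis, under Number of Participants, says "we will compare differences in processes, utilization, and outcome endpoints across the two sites", and Section 5.2 lists "differences across the two sites with processes, utilization, and outcome endpoints". The synopsis list of secondary outcomes does not include utilization, and Sections 7, 7.2 and 7.3 do not mention it.

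**The concern.** Read literally, the bullet attaches hospitalizations and ED revisits to the months before the index visit, where the word revisit makes little sense. An abstractor could ask whether an admission on day 20, an ED visit on day 60 and an ED visit four months earlier all count towards one measure.

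Two things would be at stake. First, events before the index visit cannot be affected by ED screening, so a rate that mixes them with later events could not support the planning of a later trial, which Section 7.1 gives as the use of the results. Second, each site abstracts its own charts. If the two sites read the bullet differently, the difference in reading could appear as a difference in utilization between sites. The telephone schedule adds follow-up times that do not match 30 days, with no rule for settling disagreement between sources.

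**Working it through.** The plan states no utilization rate, power or derived sample size, so there is no figure to reproduce. The check has two parts: what pooling would do, and whether the plan calls for pooling.

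**Size if the windows were pooled.** Inputs from Section 6.1.1: 30 days after the visit, and 6 months before it, taken as 183 days.

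- Share of days before the visit: 183 / (183 + 30) = 183/213 = 86%.
- Share of events before the visit if the post-visit daily rate is twice the earlier rate (assumption): 183 / (183 + 60) = 75%. If three times (assumption): 183 / (183 + 90) = 67%.
- Proportion with at least one event = 1 - exp(-rate × days / 365.25), with an assumed constant event rate per person-year:

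| Assumed rate | 30 days after | 91 days after | 183 days before | Pooled 213 days | Pooled / 30-day |
|---|---|---|---|---|---|
| 0.5 | 4.0% | 11.7% | 22.2% | 25.3% | 6.3 |
| 1 | 7.9% | 22.1% | 39.4% | 44.2% | 5.6 |
| 2 | 15.1% | 39.2% | 63.3% | 68.8% | 4.5 |

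Suppose one site pooled and the other used 30 days. At the middle rate, with 50 subjects per site, the counts would be about 50 × 0.442 = 22 and 50 × 0.079 = 4. Pooling would therefore matter, and a split reading between sites would produce a conspicuous gap.

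**Does the plan call for pooling?**

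- The lead-in to the list speaks of rates in the plural. Other bullets also hold more than one measure: one covers both referral and completion, another both dementia and mild cognitive impairment. One bullet is not one rate.
- The bullet gives a post-visit window of 30 days, and the sentence above it names the electronic record as source. Section 1.1 cites 30-day ED returns as background, and Section 8.4 lists readmission records among the source documents. Both fit a 30-day outcome.
- A look-back of 6 months is a usual way to describe prior use. It comes from the chart, so the missing Day 0 mark in Table 1 is no obstacle.
- No section combines the two periods in one figure.

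**The telephone times.** The first call may fall before day 30. Counting permitted days, that is days 7-29 of days 7-42, 23/36 = 64%, or days 1-29 of Table 1's Day 1-45, 29/45 = 64%. These are shares of calendar days; the documents give no distribution of calls. The first call alone could not supply a 30-day outcome, but the plan does not ask it to: the chart and the Month 3 call both cover day 30. A 30-day measure within about 3 months of participation (Section 4.1) is not a conflict.

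**What the number feeds.** Section 7.2 names the quantities to be measured: the proportion at risk, the number referred and the number diagnosed. Utilization is not among them. Section 4.2 says no hypotheses are tested, Section 6.2 gives no assignment, and no control group is described, so utilization yields no controlled estimate of intervention effect under any window. For one site at the middle assumed rate, the approximate 95% half-width around 7.9% is 1.96 × √(0.079 × 0.921 / 50) = 7.5 percentage points. The site comparison is a rough description even with a perfect definition.

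**The case for a change.** The strongest opposing case is that the split into history and outcome is never written down. Section 4.2.2 makes utilization a variable for the secondary objectives, the synopsis and Section 5.2 plan to compare it between sites, and no section gives its unit or says how chart and telephone data combine. Training and the five gold-standard abstractions in Section 8.2 help only if the target is clear. The choice of follow-up window also matters: with an assumed 30-day risk of 20% in 100 subjects, 20 would have an event by day 30. By day 90 the number would be 20 with no later events, 36 if the hazard halves (1 - 0.8² = 0.36), or 49 if it stays constant (1 - 0.8³ = 0.488).

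Three parts of this stand: the bullet is badly worded, the unit is not given, and the rule for telephone reports is missing. The window argument carries less weight, because the bullet itself says 30 days and day 90 is not a chart-review utilization window in the plan. Adding a day-90 chart outcome would be a preference. Limiting the outcome to ED revisits and hospitalizations would also drop other outpatient use that the bullet now includes. The worry about differing site readings is reduced by the single REDCap database with central design and data management (Sections 6.1.1 and 8.4), where dated events or separate fields for the two periods are the obvious layout.

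**Conclusion.** No change to the plan is needed. The bullet is a clerical run-on, and the missing unit and telephone rule are details that analysts would settle when building the database. Following the text, they would report 30-day post-visit utilization from the chart and the 6-month prior history as separate descriptions, with telephone reports as a supplement.

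The 86%, 75% and 67% figures, and the 4.5- to 6.3-fold inflation, arise only under a pooled analysis that no section proposes; all but the 86% share of days also rest on assumed event rates. No sample size, power figure or named test depends on utilization. The conclusion assumes that the two periods are kept apart in the data, which the plural rates, the stated 30-day window and the named chart source all support.
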